#### **4.2.4 Body Surface Area of AD**

The body surface area of AD will be summarized descriptively (N, mean, SD, median, minimum and maximum) for the absolute BSA, change, and percent change from baseline by visit. Change will be computed as the timepoint score – baseline score. Percent change as  $100 * \text{change} \div \text{baseline}$ .

### **4.3 Safety Analyses**

The comprehensive safety analysis is based on all subjects in the Safety population.

The following sections detail the summaries performed on the safety data. Additional data handling rules including those for imputation of partially missing dates will be provided in a separate SAP document pertaining to data handling and programming specifications.

The baseline scores for vital signs, laboratory assessments and ECGs will be the last non-missing value collected on or before the date of the first application of study medication. This baseline will also be used for calculating change from baseline.

#### **4.3.1 Adverse Events**

Adverse events will be coded using the MedDRA dictionary V21.1 and will be categorized by system organ class (SOC) and preferred term (PT). Only treatment emergent adverse events will be included in summary tabulation. All adverse events, including those that are not considered treatment emergent, will be included in the data listings.

To differentiate the study period in which an Adverse Event occurred, three categories will be defined based upon onset date. Adverse Events that had onset dates prior to the first application of study medication will be considered "prior". Adverse events with onset dates on or after the first application of study medication and within 30 days following the last application of study medication will be considered "on therapy" or equivalently "treatment emergent". Events with onset dates more than 30 days after the last application of study medication will be considered as "post-therapy".

Frequency tabulations will be presented by MedDRA SOC and preferred term, for all adverse events; study treatment-related, adverse events resulting in discontinuation of study treatment, serious adverse events and adverse events by maximum severity. Adverse events resulting in discontinuation will be those with 'action taken' recorded as 'drug withdrawn'.

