⁷ All subjects will be required to have virology testing for HepB (HBsAG), HCV(antibody), and HIV (antibody). If a subject demonstrates to have serological evidence HepB (HBsAG), HCV (antibody) or HIV (antibody), the subject will not be allowed to enroll to the study.

⁸ Canfield staff will review all photographs within 2 days of the photographs being submitted. If a re-take is required, Canfield will notify the site and the re-take photographs will need to be performed within 7 days of the visit. Prior to enrollment to the study, each subject's Visit 1 photos will be reviewed by a panel of board certified dermatologists to ensure that the subject's target areas for treatment meet the study entry criteria. In cases where the photographs do not properly characterize the disease (due to flashback and whitening on the photographs) the subjects will be allowed to enroll to the study based upon the Principal Investigator's clinical assessment of the subject.

⁹ At visit 2, following confirmation that the subject is approved for enrollment to the study, the site will weigh and dispense supplies of ATI-502 study medication and disposable droppers to the subject for at home application of the study medication.

¹⁰ All subjects will have their first application of study medication applied in the clinic during Visit 2. Subjects will continue to apply ATI-502 Topical Solution, 0.46% to all target areas twice a day for 4 weeks (Day 28) unless the subject meets the criteria for treatment interruption. If new areas of AD develop, subjects will be allowed to treat these areas with the ATI-502 study medication.

¹¹ Sites will be required to review with each subject the proper application of the study medication and remind that they must refrain from exercise that may cause excessive sweating, bathing or swimming for a period of 6 hours after the application of study medication. Subjects are also to be reminded that they may not apply moisturizers, emollients, or sunscreen to target AD areas during protocol treatment.

¹² All non-serious AEs will be collected from the time of first study medication application until the final study visit. Serious AEs will be collected from the time of consent through the final study visit.

¹³ A final safety follow up visit will be conducted at week 8 (Visit 6). For those subjects that discontinue the study early, they must return to the clinic 4 weeks following the last study medication application for a final safety visit.

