13.2. Adverse and Serious Adverse Events

13.2.1. Definition of Adverse Events

13.2.1.1. Adverse Event (AE)

An AE is the development of an undesirable medical condition or the deterioration of a pre-existing medical condition following or during exposure to a pharmaceutical product, whether or not considered casually related to the product. In clinical studies, an AE can include an undesirable medical condition occurring at any time, including baseline or washout periods, even if no study treatment has been administered.

The investigator should, when certain, report a diagnosis rather than the signs, symptoms or clinically significant abnormal laboratory values associated with the AE. Otherwise, signs, symptoms or abnormal laboratory values may be used to describe the AE.

Any CS abnormality discovered prior to the first study medication treatment should be reported as medical history, not as an AE.

All AEs that occur from the time of first study medication application (Visit 2) until 30 days after last study medication application must be documented in the subject's source documents and in Aclaris' EDC system.

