13.3.5. Procedure for reporting a serious adverse event

Upon becoming aware of a SAE occurring during the AE reporting period, whether or not related to the study medications, the investigator must:

1. Take the appropriate medical action to ensure the subject’s safety.
2. Immediately inform the Safety Monitor of the SAE by email, ensuring that the subject information is deidentified (only subject initials and subject number) to: **ProPharma, Email: [contact]**.
3. Print a copy of the email confirmation from ProPharma and place in the study file.
4. Within 24-hours complete, as fully as possible, an AE eCRF and an SAE form; e-mail the forms and any other relevant information (e.g., concomitant medication eCRF, medical history eCRF, laboratory test results) to ProPharma.
5. Monitor and document the progress of the SAE until it resolves or, if not resolved after the subject’s last study visit, until in the opinion of the investigator the AE reaches a clinically stable outcome with or without sequelae AND the investigator and Aclaris

Therapeutics, Inc. Safety and Medical Monitor agree that the SAE is satisfactorily resolved.

6. Inform the Aclaris Therapeutics, Inc. Safety Monitor of SAE updates, via telephone, followed by an SAE form update sent by e-mail.
7. Comply with the appropriate regulatory requirements and Aclaris Therapeutics, Inc. instructions regarding reporting of the SAE to the responsible Institutional Review Board (IRB) or Ethics Committee (EC).

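### The SAP's treatment-emergent definition rests on onset date alone and has no limb for worsening on drug, so a few deteriorations could drop out of the adverse event frequency tables.

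*SAP*

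**What the plan says.** SAP 4.3.1 states that "three categories will be defined based upon onset date". The first class is defined by the sentence "Adverse Events that had onset dates prior to the first application of study medication will be considered" prior. The second takes events with onset "on or after the first application of study medication and within 30 days following the last application of study medication will be considered" on therapy, which the SAP equates with treatment emergent. Later onsets are post-therapy. The section then restricts the tables: "Only treatment emergent adverse events will be included in summary tabulation". The rest are not discarded: "All adverse events, including those that are not considered treatment emergent, will be included in the data listings".

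The protocol's definition of an AE is wider than new onset. Section 13.2.1.1 includes "the deterioration of a pre-existing medical condition following or during exposure to a pharmaceutical product". The same section sends clinically significant abnormalities found before the first treatment to medical history, and 13.1.2 and 13.1.4 repeat this for vital signs and ECG.

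Collection periods differ by seriousness. Non-serious AEs are collected from the first application (Table 2 footnote 12; 13.3.1). For serious events the footnote reads "Serious AEs will be collected from the time of consent through the final study visit". Under 13.3.5 a serious event is followed to its outcome, and changes are reported by telephone, "followed by an SAE form update sent by e-mail".

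**The concern.** A treatment-emergent definition usually has two limbs: events that start on drug, and events that started earlier but got worse on drug. SAP 4.3.1 has only the first. The protocol counts deterioration as an AE, so the tabulation rule makes no explicit provision for one of the two kinds of event that the protocol asks sites to report.

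This matters because safety and tolerability is the primary outcome and the study is single-arm and open label. The AE tables are therefore read at face value, with no comparator to share the same bias. All subjects also enter with moderate or severe atopic dermatitis of at least 6 months' standing, a disease the protocol introduction describes as one that flares. Worsening of a condition with an old start date is foreseeable. A record wrongly classed as prior leaves the overall, related, serious, discontinuation and maximum-severity tables together.

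**Working it through.** The plan has no figure to reproduce: the study is descriptive and the sample of 30 has no formal basis (SAP 4.4). The check applies the classification rule to the records the protocol can generate.

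**The rule (SAP 4.3.1).** Let d be the onset date on the AE record, F the date of first application and L the date of last application.
- d < F: prior, listed only
- F ≤ d ≤ L + 30 days: treatment emergent, tabulated and listed
- d > L + 30 days: post-therapy, listed only

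No term depends on a change in severity or seriousness.

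**Applied to four illustrative records**

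| Record | Onset entered | Class | In AE tables? |
|---|---|---|---|
| A. Condition in medical history worsens on Day 10; AE dated at the worsening | Day 10 | treatment emergent | yes |
| B. Same condition; AE dated at the start of the condition | before Day 1 | prior | no |
| C. Serious event starts on Day -5, worsens on Day 6; same record updated, onset kept | Day -5 | prior | no |
| D. Same serious event; worsening entered as a separate record | Day 6 | treatment emergent | yes |

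**Which records are to be expected?** A is the normal case. Protocol 13.2.1.1 places the earlier condition in medical history, and 13.3.1 starts non-serious AE reporting at the first application. The reportable event is then the deterioration itself, which happens after dosing. B needs a site to enter the start of the condition instead. Neither supplied document says which date is the onset of a deterioration, so B is not ruled out.

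C can arise because serious events are collected from consent and screening lasts up to 14 days (protocol 7.3). Whether C or D results depends on whether the site updates the existing record or opens a new one. Protocol 13.3.5 describes updating and does not say what happens to the onset date. The SAP's own prior class shows that records with a pre-dose onset are expected.

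**Scale.** Fall in overall incidence when k subjects lose their only treatment-emergent event, with N in the Safety Population: 100 × k / N percentage points.
- k = 1, N = 30: 100 × 1/30 = 3.3
- k = 2, N = 30: 100 × 2/30 = 6.7
- k = 3, N = 30: 100 × 3/30 = 10.0
- One lost serious event, if it was the only one: from 1/30 (3.3%) to 0/30

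Protocol 7.7 replaces subjects who do not complete all visits, while SAP 4.1.1 keeps everyone with at least one application in the Safety Population. With r replaced subjects who were dosed, N = 30 + r and the step is 100/(30 + r), so 3.3 points is the upper limit per subject if 30 or more are dosed. If r = 3 (an assumption for illustration), it is 100/33 = 3.0.

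A subject with another treatment-emergent event stays in the overall row. What can change for that subject is the row for the lost term or the maximum-severity category.

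**Direction.** The missing limb can remove records from the tables but cannot add any. Any error is therefore towards fewer or milder reported events.

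**The case against.** The strongest reply is that the SAP dates the adverse event, not the underlying condition. For a pre-existing condition the AE is the deterioration, which begins after dosing, so the existing sentence already classes it as treatment emergent. On this view record B is a data-entry error and not a consequence of the SAP. This largely stands. A reader might infer that any condition present before dosing which worsens on drug is automatically prior; the documents do not support that, because the medical-history rule and the start of non-serious collection lead normally to record A. What remains is that no supplied text fixes the onset date of a deterioration, and that the serious-event route does not depend on an entry error.

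A reader might also infer that all the primary safety output is affected. It is not. Protocol 14.1 treats all safety and tolerability parameters as primary. The vital-sign summaries, ECG shift table and laboratory summaries (SAP 4.3.3 to 4.3.5) do not use the AE onset class. Only the AE frequency tables are exposed.

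Nor would worsening of the dermatitis be visible only in a listing. EASI, SPA and BSA are summarised by visit with change from baseline, minimum and maximum (SAP 4.2), so deterioration would show there. Those tables do not carry relatedness, seriousness or discontinuation, and the PGA and SAD summaries count only favourable states or improvement. They compensate in part.

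The serious-event route is narrow. It needs a serious event in a short screening period, a subject who still meets the entry criteria, and later worsening on drug.

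Finally, SAP 4.3 defers further data-handling rules to a separate document. Neither it nor the eCRF instructions are among the documents reviewed, and either could settle the dating. SAP 4.3.1 does, however, state its definition without exception and without a cross-reference for worsening.

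**Conclusion.** The gap is real and minor. As written, SAP 4.3.1 misclassifies two kinds of record: a serious event that began between consent and first application and worsened on drug under the same record, and a deterioration dated at the start of the condition. Either would be missing from the AE frequency tables and visible only in the listings.

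The effect on overall incidence is at most 3.3 percentage points per affected subject with 30 or more dosed, and it can only flatter the safety profile. How many subjects would be affected cannot be derived, because the documents give no rate; the collection rules suggest few.

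The conclusion assumes that sites follow the medical-history rule for pre-dose findings, and that the separate data-handling document contains no worsening rule. If it does contain one, all that is left is a missing cross-reference.

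**What to change.** In SAP 4.3.1, define treatment emergent as either of:
- onset on or after the first application and no later than 30 days after the last; or
- onset before the first application, with an increase in severity or a change to serious within that same window. Classify these events by the date of worsening.

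In the eCRF instructions, state that a deterioration is entered as its own AE record with the date of worsening as its onset. This line does most of the work, since such a record already falls in the right class; the SAP limb then covers any record that was updated rather than split. If the data-handling document already has such a rule, cite it in 4.3.1.

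The cost is one SAP sentence and one instruction line, with no change to visits, treatment or sample size. The downside is that the reported treatment-emergent rate may rise slightly.

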7.4. Treatment Assignment

This is an open label study. All subjects will be treated twice daily for 4 weeks with ATI-502 Topical Solution, 0.46%.

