13.1.4. Electrocardiogram (ECG)

Standard 12-lead ECGs will be performed by a qualified staff member at Screening (Visit 1), Day 8 (Visit 3), Day 15 (Visit 4), Day 29 (Visit 5) and Day 56 (Visit 6/End of Study). The ECGs must be obtained using a standard 12-lead ECG with a 10mm/mV amplitude, at 25mm/sec and a 5 to 10 second duration. To ensure a steady heart rate the subject must rest quietly in the supine position for at least 5 minutes prior to performing the ECG.

A central cardiology laboratory will provide ECG equipment, supplies and site training. In addition, the central cardiology laboratory will process ECGs received by the sites and report results via a secure study portal. The ECG results will be interpreted by a qualified health professional (evaluator) and the interpretation reported either directly on the tracing or in a separate report. The evaluator will interpret the results of every ECG and define the ECG as “normal” or “abnormal”. Variations such as minor ST changes (i.e., <0.5mm depression) and early re-polarization are considered normal.

The investigator must review the evaluator’s interpretation of each subject’s screening ECG prior to Visit 2. The investigator will review the evaluator’s interpretation of all ECG reports in a timely manner and comment on the clinical relevance of any result that is defined by the evaluator as abnormal.

Any abnormalities that are, in the opinion of the investigator, clinically significant, must be reported as history if found prior to the start of the first dose of study medication or as an AE if found after the start of the first dose of study medication

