## 2. STUDY DESIGN

This is an open label, multicenter, phase 2a study designed to evaluate the safety and tolerability of ATI-502 Topical Solution, 0.46% in male and female subjects with a diagnosis of AD as defined by the Hanifin and Rajka criteria. Based on the 5-point Physician's Global Assessment (PGA) scale, subjects must have a score of 3 (moderate) or 4 (severe). Subjects will be required to apply ATI-502 study medication to their identified AD treatment areas twice a day (BID) for a total of 4 weeks. Subjects will be allowed to treat new disease areas with ATI-502 Topical Solution, 0.46% if they appear after Visit 2. All subjects will be required to complete a safety follow up visit 4 weeks post last study medication application.

A total of 30 evaluable subjects who are  $\geq$  18 years of age with a clinical diagnosis of moderate or severe AD will be enrolled to the study.

Safety and tolerability will be evaluated by assessment of adverse events, physical examinations, vital signs, ECGs and clinical laboratory tests.

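### The SAP's adverse event tables pool the treatment month with the off-drug follow-up month under the label 'on therapy', so they cannot show whether events began during or after dosing

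*SAP*

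**What the plan says.** SAP 4.3.1 gives the purpose of its categories: "To differentiate the study period in which an Adverse Event occurred, three categories will be defined based upon onset date". They are:

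- *prior*: onset before the first application;
- *on therapy*, equated with treatment emergent: events with onset on or after the first application and "within 30 days following the last application of study medication will be considered" to be in this category;
- *post-therapy*: onset later than that.

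The section then restricts the tables: "Only treatment emergent adverse events will be included in summary tabulation". The planned output is described as "Frequency tabulations will be presented by MedDRA SOC and preferred term, for all adverse events", followed by treatment-related events, events leading to discontinuation, serious events and maximum severity. None of these is split by whether onset fell during or after dosing. All AEs appear in the listings.

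Protocol Table 2, footnote 10, sets application "twice a day for 4 weeks (Day 28) unless the subject meets the criteria for treatment interruption", and protocol 7.4 also gives 4 weeks. On follow-up, SAP section 2 says: "All subjects will be required to complete a safety follow up visit 4 weeks post last study medication application". The schedule in both documents puts Visit 6 at week 8, Day 56, with a +7 day window.

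Protocol 14.1 makes safety and tolerability the primary analysis variables. It says all data will be summarized by visit and names treatment-emergent AEs as its example of binary data. SAP 4.3.1 plans no by-visit AE table, and SAP 4.5 does not list this as a change.

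**The concern.** The categories do not do what SAP 4.3.1 says they are for. Nearly all of a completer's off-drug follow-up falls in the category named *on therapy*, and *post-therapy* is almost empty by construction.

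AE incidence is a main component of the primary outcome in a single-arm, open-label study. A reader of the AE tables will want to know whether events began while the solution was being applied or in the month after it stopped. The tables cannot answer that. An event starting two weeks after the last application is counted beside one starting on Day 3, under a label that says the subject was on therapy. The by-visit presentation in protocol 14.1 would have kept some of this timing.

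**Working it through.** **Inputs**

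- Last application: Day 28 (protocol Table 2, footnote 10; 4 weeks in protocol 7.1 and 7.4).
- Visit 5: Day 29 ± 3. Visit 6: Day 56 + 7 (schedule of assessments).
- End of the treatment-emergent window: last application + 30 days (SAP 4.3.1).
- AE reporting end: 30 days after last application (protocol 13.2.1.1) or last study visit (protocol 13.3.1). The two statements differ, so both ends are shown.

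**Step 1. The plan's own timeline.** 28 treatment days + 28 follow-up days = Day 56, which matches Visit 6. The latest Visit 6 is 56 + 7 = Day 63.

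**Step 2. Off-drug share of the window.** Share = (E − L)/E, where L is the day of last application and E is the earlier of Visit 6 and L + 30.

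| Last application | Visit 6 | Window end | Off-drug days | Share |
|---|---|---|---|---|
| Day 28 | Day 56 | Day 56 | 28 | 28/56 = 50.0% |
| Day 28 | Day 63 | Day 58 | 30 | 30/58 = 51.7% |
| Day 26 | Day 56 | Day 56 | 30 | 30/56 = 53.6% |
| Day 32 | Day 56 | Day 56 | 24 | 24/56 = 42.9% |

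The last two rows take the final application on the day of Visit 5, at the edges of its window.

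For a subject who stops early and is seen 28 days later, the share is larger: 28/49 = 57.1% (stop on Day 21), 28/42 = 66.7% (Day 14), 28/35 = 80.0% (Day 7).

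**Step 3. What is left for *post-therapy*.** With last application on Day 28, the category starts on Day 59. It covers 0 days if Visit 6 is on Day 56, and 63 − 58 = 5 days if Visit 6 is on Day 63.

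**Step 4. Effect on a reported percentage (illustration only).** Assume a constant background rate, no drug effect and equal ascertainment in both periods. None of these comes from the documents. With incidence b over 28 days, pooled incidence is 1 − (1 − b)^(T/28).

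- T = 56: 1 − 0.90² = 0.190.
- T = 58: 1 − 0.90^(58/28) = 0.196.

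So b = 10% is reported as 19% to 20%. In 30 subjects that is 3.0 expected subjects against 5.7 to 5.9. The denominator, all treated subjects, is the same in both cases, so the percentage can rise but not fall.

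**Step 5. Sensitivity to a conflict in the protocol.** Protocol 7.3 gives a maximum duration of study treatment of 63 days, against 4 weeks elsewhere. If 63 days were read as dosing time, the share would be 30/93 = 32.3%. These passages must be reconciled. The results above use the 4-week statements.

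**The case against.** The strongest reply is that no planned number is wrong. The 30-day limit agrees with protocol 13.2.1.1 for AEs and 13.2.1.2 for serious AEs. *On therapy* is defined in the text as equivalent to treatment emergent. All AEs are listed, and with 30 subjects onset can be compared with the last application by eye. A treatment-related table is planned, and investigators weigh temporal relationship when judging causality. Disease worsening after stopping would also show in the efficacy scores at Visit 6. All of this stands. It means that no data are lost and that the window itself is sound. It does not give the AE tables the timing they lack, and it does not make the label accurate.

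Three stronger readings are tempting, and the documents do not support them:

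- *Pooling dilutes on-drug events.* SAP 4.3.1 plans frequency tables over all treated subjects, not rates per exposure time. Extra follow-up leaves the denominator unchanged.
- *The follow-up month is a built-in control period.* AEs are elicited by a non-directive question at each visit (protocol 13.3.4). Treatment has three such visits (Days 8, 15 and 29) and follow-up has one, about four weeks later. Fewer onsets in follow-up could reflect fewer contacts and longer recall, and the periods are also ordered in time.
- *The treatment-emergent window is too long.* It matches the protocol's collection period, and nothing here argues for shortening it.

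A split also has complications. A subject with the same preferred term in both periods counts twice across columns, and time from first to last application includes any interruption under protocol 11.3.

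**Conclusion.** The point holds as a matter of labelling and presentation, not as an error in the treatment-emergent window. About half of the window called *on therapy* is off-drug for a completer: 50% to 52% on the nominal schedule, about 43% to 54% within the visit windows, and more for early stoppers. *Post-therapy* covers at most about 5 days when the last application is on Day 28. The AE tables therefore cannot separate onset during dosing from onset afterwards, and this departs from protocol 14.1 without being recorded in SAP 4.5.

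The shares rest on 4 weeks of dosing. The rise from 10% to 19% or 20% rests on the assumed constant rate and is not a forecast for this trial.

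The point is confined to the AE tables. Vital signs and laboratory values are already summarized by visit, so Visit 6 stays separate there. It is worth acting on because the change is cheap and makes the primary safety summary easier to interpret.

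**What to change.** In SAP 4.3.1:

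1. Keep treatment emergent, to 30 days after the last application, as the total. Stop using *on therapy* as its synonym.
2. In the SOC/preferred term, treatment-related, serious and maximum-severity tables, add two columns beside the total: onset from first through last application, and onset after the last application to the end of the window. The discontinuation table can stay as it is, since an action of drug withdrawn in practice concerns subjects still being dosed.
3. State that a subject may count in both columns, so they need not sum to the total, and that maximum severity is taken within each period.
4. State that the treatment-period column includes any interruption time.
5. State that the contrast is descriptive only, because the periods are ordered in time and follow-up has one visit against three during treatment.

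In SAP 4.5, record that AEs are shown by period rather than by visit as in protocol 14.1.

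The cost is SAP wording and two table columns. Classification by onset date is already planned, so no new data are needed. The downsides are small cells at 30 subjects and non-additive columns.
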